5.6 Informed Consent

The retrospective control group of this study meets the requirements for waiver of consent, as defined in FDA guidance document titled: "IRB Waiver or Alteration of Informed Consent for Clinical Investigations Involving No More Than Minimal Risk to Human Subjects; Guidance for Sponsors, Investigators, and Institutional Review Boards", released July 2017. As approved by the IRB, documentation of informed consent will not be required for the retrospective control group involving only medical chart review and collection of de-identified historical information.

A written informed consent will be required for the prospective groups in the study. All items of the Informed Consent will be explained in a way that is easily understandable for the patient. The patient will be given adequate time to read through the Informed Consent, and they will be given adequate time and privacy to consider the decision of whether or not to sign the Informed Consent Form. Once all of the patient's questions have been answered and the Informed Consent Form signed, the patient will be

enrolled as a study subject, at which time the subject will be assigned a unique study identification number.

5.7 Withdrawal of Subjects

Informed consent discussions will explicitly include emphasis that neither patient enrollment nor patient withdrawal from the study will result in any alterations to the standard clinical care that he/she will receive. Subjects may elect to withdraw from the study at any time.

In order to obtain the required number of subjects at each clinical site, if a subject withdraws or is withdrawn from the study, the site staff should make arrangements to enroll an additional subject as a replacement. See Section 7.7 Handling Missing Data in Statistical Analysis for details regarding how data from withdrawn subjects will be handled when analyzing study outcome measures.

6 STUDY PROCEDURES

6.1 Control Group

6.1.1 Retrospective Control Group

Approximately [REDACTED] will be retrospective data collected from the site's medical records. The retrospective data will be collected by designated site personnel only and reported to the sponsor via CRFs.

6.1.2 Prospective Control Group

Approximately [REDACTED] will be prospective data collection from subjects undergoing surgery. Prospective subjects enrolled in the control arm will be treated per individual clinical site's standard of care (SOC) procedures during and after surgery. The amount of blood transfused, amount of fluid infused, along with other study outcome measures and physiological parameters will be reported on the CRF. In Vivo SpHb and RPVi data will be automatically recorded in the study devices or through a data collection laptop. The display on the study devices will be blacked out so that anesthesiologists will be blinded to the In Vivo SpHb and RPVi monitoring throughout the surgical procedure. All blood transfusion and fluid infusion decisions will be made by clinician's judgment and per SOC procedures. Subjects will receive a phone call from the clinical site staff for a 30-day post-op follow-up on the subject's conditions.

6.2 Intervention Group

Prospective subjects will be enrolled in the intervention group after the control group enrollment phase has been completed. Intervention group subjects will be treated per individual clinical site's SOC procedures during and after surgery. In addition, these subjects will also be monitored with SpHb with In Vivo adjustment and RPVi monitoring devices to trigger confirmatory laboratory blood draws, which will then be used to guide standard of care blood transfusion and fluid infusion decisions. The investigator will make a determination of the threshold for blood transfusion on a case-by-case basis depending on individualized patient clinical conditions. This threshold value will be determined prior to the start of the surgical procedure and it will be recorded in the CRF. Dynamic fluid responsiveness parameters such as RPVi are already in use by many providers to guide fluid infusion decisions, but unlike RPVi, most dynamic fluid responsiveness parameters are often obtained by invasive means, along with other hemodynamic parameters. The procedure for monitoring with In Vivo SpHb and RPVi is illustrated in the

[figure not shown]
[figure not shown]
Evaluation of Impacts of Continuous Non-Invasive Intra-operative Hemoglobin and RPVi Monitoring on Intra-operative and Post-Surgical Clinical Outcomes
BIGT0001 version 2

Flow Diagram (Figure 3). The amount of blood transfused, amount of fluid infused, the time of blood draw, the value of tHb, along with other study outcome measures and physiological parameters will be reported on the CRF. In Vivo SpHb and RPVi data will be automatically recorded and stored in data files. All blood transfusion and fluid infusion decisions will be made by clinician's judgment with additional supplemental information provided by In-Vivo SpHb and RPVi parameters. Subjects will receive a phone call from the clinical site staff for a 30-day post-op follow-up on the subject's condition.

In Vivo SpHb and RPVi readings that signal a change in the patient's status shall be confirmed with a confirmatory blood draw, as shown in the Intervention Group Study Procedures Flow Diagram (Figure 3). At all times, anesthesiologists shall use their clinical judgment and standard of care tools to make blood transfusion and fluid infusion decisions.

6.3 Intervention Group Study Procedures Flow Diagram

Evaluation of Impacts of Continuous Non-Invasive Intra-operative Hemoglobin and RPVi Monitoring on Intra-operative and Post-Surgical Clinical Outcomes
BIGT0001 version 2

Evaluation of Impacts of Continuous Non-Invasive Intra-operative Hemoglobin and RPVi Monitoring on Intra-operative and Post-Surgical Clinical Outcomes

BIGT0001 version 2

6.4 SpHb In Vivo Adjustment and RPVi

6.4.1 In Vivo SpHb:

The SpHb In Vivo Adjustment feature allows clinicians to manually adjust the SpHb parameter to match that of a corresponding laboratory reference for continuous trending. In order to utilize the In Vivo Adjustment feature of SpHb, the device requires the user to enable this feature and input an offset value. The offset value is the difference between a laboratory tHb value from analyzing a blood sample and the displayed SpHb value when the blood sample was drawn. After the offset value has been entered, the device will incorporate the offset as it computes SpHb values. [REDACTED]

6.4.2 RPVi:

6.5 Laboratory Evaluation

Throughout the study procedure, venous or arterial blood draws will be taken at the anesthesiologist's discretion either as confirmatory blood draws based on the triggers from the Masimo monitor or based on standard of care clinical judgment in support of blood transfusion or fluid infusion decisions. [REDACTED]

[REDACTED] Blood samples will be analyzed by the local laboratory with a co-oximeter or an arterial blood gas (ABG) machine. Data on any hemoglobin measurements and/or ABG performed during the surgery will be recorded on the CRF.

6.6 Follow-Up Procedures

For each subject, this study consists of only one visit which occurs on the day of surgery. The only follow-up being performed is a phone follow-up 30 days after the day of surgery. Subjects will receive a

Evaluation of Impacts of Continuous Non-Invasive Intra-operative Hemoglobin and RPVi Monitoring on Intra-operative and Post-Surgical Clinical Outcomes

BIGT0001 version 2

phone call from the research staff to check on subjects' condition and gather information as required in the Case Report Form. This follow-up provides information for secondary outcome measures only.

[figure not shown]
6.7 Schedule of Activities

Table 3. Study activities and relative time for each subject.

Schedule	Study Activities
Day 0 – 1	Screening
Day 1	Informed Consent
Day 1	Enrollment, Study Data Collection
Day 30 - 40	Subject Follow-Up Phone Call, Case Report Form Completion

7 SAMPLE SIZE AND STATISTICAL CONSIDERATIONS

7.1 Power Analysis and Sample Size Determination

[figure not shown]
7.2 Prior Study Data

Evaluation of Impacts of Continuous Non-Invasive Intra-operative Hemoglobin and RPVi Monitoring on Intra-operative and Post-Surgical Clinical Outcomes

BIGT0001 version 2

The figure consists of a 9x8 grid of black and white bars. The first 8 rows have 8 columns each, while the bottom row has 7 columns. The bars are composed of black segments of varying lengths and white segments. The first row has a 3-unit bar, a 1-unit bar, a 2-unit bar, a 2-unit bar, a 1-unit bar, a 1-unit bar, a 1-unit bar, and a 1-unit bar. The second row has a 4-unit bar, a 1-unit bar, a 2-unit bar, a 2-unit bar, a 2-unit bar, a 1-unit bar, a 1-unit bar, and a 1-unit bar. The third row has a 5-unit bar, a 1-unit bar, a 2-unit bar, a 2-unit bar, a 1-unit bar, a 1-unit bar, a 1-unit bar, and a 1-unit bar. The fourth row has a 6-unit bar, a 1-unit bar, a 2-unit bar, a 2-unit bar, a 2-unit bar, a 1-unit bar, a 1-unit bar, and a 1-unit bar. The fifth row has a 7-unit bar, a 1-unit bar, a 2-unit bar, a 2-unit bar, a 2-unit bar, a 2-unit bar, a 1-unit bar, and a 1-unit bar. The sixth row has a 8-unit bar, a 1-unit bar, a 2-unit bar, a 2-unit bar, a 2-unit bar, a 2-unit bar, a 1-unit bar, and a 1-unit bar. The seventh row has a 9-unit bar, a 1-unit bar, a 2-unit bar, a 2-unit bar, a 2-unit bar, a 2-unit bar, a 1-unit bar, and a 1-unit bar. The eighth row has a 10-unit bar, a 1-unit bar, a 2-unit bar, a 2-unit bar, a 2-unit bar, a 2-unit bar, a 1-unit bar, and a 1-unit bar. The bottom row has a 11-unit bar, a 1-unit bar, a 2-unit bar, a 2-unit bar, a 2-unit bar, a 2-unit bar, a 1-unit bar, and a 1-unit bar.

7.4 Adjusting For Intra-class Correlation

Assuming that the intra class correlation ($ICC = \rho$) is 0.001, the estimated sample size from the simulation is adjusted for the design effect (DE) to account for correlation within each Site.

Adjusted Sample Size = Estimated Sample Size x DE

Where $DE = 1 + (m - 1)\rho$ and m equal to the average estimated sample size per site.

[figure not shown]
Table 5. Sample Size Results

Evaluation of Impacts of Continuous Non-Invasive Intra-operative Hemoglobin and RPVi Monitoring on Intra-operative and Post-Surgical Clinical Outcomes

BIGT0001 version 2

CONFIDENTIAL AND PROPRIETARY
© 2021 Masimo Corporation (Unpublished)
All Rights Reserved

Page 23 of 45

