3 STUDY DESIGN AND OBJECTIVES

3.1 Overview of the Study Design

Evaluation of Impacts of Continuous Non-Invasive Intra-operative Hemoglobin and RPVi Monitoring on Intra-operative and Post-Surgical Clinical Outcomes

BIGT0001 version 2

This is a sequential, stepped-wedge, controlled, multi-center study with a total enrollment of approximately 2304 subjects across all participating sites (See Figure 1). There will be six clinical sites participating in this study. One interim analysis and one final analysis will be performed.

All control group subjects at each participating clinical site will be enrolled prior to the enrollment of the intervention group subjects. [REDACTED]

The retrospective control group will involve the collection of historical medical records from patients who had undergone similar surgeries as the prospective control and intervention groups. Subjects for the retrospective control group will be selected at random from a list of eligible patients. Refer to Section 5.1.2 Subject Selection Methods for details on selection of the retrospective control subjects.

The prospective control group will be treated as per standard of care. The prospective control group subjects will be given the study device in order to collect In Vivo SpHb and RPVi data during the surgery for post-study analysis; the recorded In Vivo SpHb and RPVi measurements will not be viewable to the investigators, rendering them blinded to In Vivo SpHb and RPVi data during the surgery.

The prospective intervention group will be treated as per standard of care with the addition of non-invasive In Vivo SpHb and RPVi monitoring via the study device as per the procedure stated in the Study Procedure section in this CIP.

Subjects for both prospective control group and intervention group will be enrolled on a convenience sampling basis from hospital patients who are already scheduled for surgery. Refer to Section 5.1.2 Subject Selection Methods for details on selection of the prospective subjects.

Patients' characteristic data such as demographics, skin tone, ASA status, surgery type, etc. will be recorded as part of the study Case Report Form (CRF) and analyzed for comparability between control and intervention groups.

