3.2 Rationale for the Study Design

The stepped-wedge design will minimize potential treatment contamination between control and intervention participants, by completing the enrollment of the control group before enrollment of the intervention group. The stepped-wedge design is being employed to mitigate for any potential temporal variability in patient population and variability in institutional standard of care procedures.

[figure not shown]

Figure 1. Overview of study design as a stepped wedge implementation. [REDACTED]

[REDACTED] Intervention phase each consist of 100% prospective cases. Note: the length of the Control and Intervention phases may be different from site to site depending on enrollment rate.

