7.6 Data Analysis

7.6.1 Interim Analysis

One interim data analysis and a final analysis will be performed; the interim analysis will be performed after collecting data on 281 subjects in the intervention group and 562 subjects in the control group.

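### Section 7.4 inflates the sample size by a parallel-cluster design effect, with cluster size taken before inflation, although every site in this six-site stepped wedge supplies both groups

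*Combined protocol and SAP*

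**What the plan says.** - **Design.** Section 3.1: "This is a sequential, stepped-wedge, controlled, multi-center study", with "a total enrollment of approximately 2304 subjects across all participating sites" and "There will be six clinical sites participating in this study". Sections 3.1, 5.1.2 and 5.4 have each site complete its controls before starting intervention enrolment, and successive sites start intervention about 6 weeks apart. Part of the control group is retrospective.
- **Reason for the design.** Section 3.2 says it was chosen "to mitigate for any potential temporal variability in patient population and variability in institutional standard of care procedures".
- **Inflation.** Section 7.4 assumes that the ICC "is 0.001, the estimated sample size from the simulation is adjusted for the design effect (DE"), where DE = 1 + (m − 1)ρ and "m equal to the average estimated sample size per site".
- **Analysis.** Equation 1 in Section 7.6.2.2 has a site random intercept, an intervention effect and further covariates, with demographic and clinical variables as the examples. It prints no calendar-time term. Table 6 names a Binomial-Gamma hurdle model for the primary outcome.
- **Interim and alpha.** Section 7.6.1 places the interim at "281 subjects in the intervention group and 562 subjects in the control group". Section 7.8 gives an overall one-sided alpha of 0.05 and an interim information time of 0.5.

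The base sample size, effect, variability, target power and contents of Table 5 are not visible in the public text. That is not a fault in the plan.

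**The concern.** DE = 1 + (m − 1)ρ measures the precision lost when treatment is compared between clusters. In this trial each site is its own control, so site differences largely cancel out of a control-versus-intervention contrast. What costs precision in a stepped wedge is different: intervention always follows control within a site, so treatment and calendar time overlap, and separating them uses up information. The printed factor measures neither situation.

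Two things are at stake. If calendar period enters the primary model, the inflation may be much too small, and a null result could simply reflect low power. If it does not, the inflation has no basis, and the stated justification for 2304 does not describe the planned analysis.

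A lesser issue is that the number of sites is fixed at six. Raising the total raises m, so a formula that uses m before inflation understates its own design effect.

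**Working it through.** **1. The plan's figure.** The base n0 is not visible, so 2304 cannot be reproduced independently. Solve backwards with m = n0/6:

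- n0 × [1 + (n0/6 − 1) × 0.001] = 2304 gives n0 ≈ 1779, m ≈ 296.4, DE ≈ 1.295.
- So 2304 is compatible with the formula as written, at an inflation of about 1.30.
- The only other base that visible figures suggest is (281 + 562)/0.5 = 1686. With m = 1686/6 = 281, DE = 1.280 and the total is 2158, which is not 2304. Both bases are carried below as a range.

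**2. Design effect for Equation 1 as printed.** Inputs: 6 sites, 2304/6 = 384 per site, ρ = 0.001. Control:intervention is taken as 2:1 (562:281 at the interim, assumed to hold at the end and within each site), so 256 and 128 per site. With the same ratio at every site, the site effects cancel and the variance is (1 − ρ)(1/768 + 1/1536). Relative to independent subjects, DE = 1 − 0.001 = 0.999. A balanced 1:1 stepped wedge in seven periods gives 1.07. Neither needs inflation by 1.30.

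**3. Design effect with calendar period.** This uses the generalised least squares variance with a site random intercept and fixed six-week periods, treating the outcome as continuous. Sites are staggered by one step, and each site's control phase is assumed to last twice its intervention phase:

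| Intervention phase | DE, ρ = 0.001 |
|---|---|
| 12 weeks | 1.76 |
| 24 weeks | 2.97 |
| 36 weeks | 4.32 |

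Sensitivity to the layout, also at ρ = 0.001:

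- Balanced six-step, seven-period wedge: 2.04. The closed-form stepped-wedge design effect agrees.
- Same seven periods at 2:1: 2.73. With half the controls placed in one earlier period common to all sites: 3.67.
- Common start with 1, 2 or 4 lead-in steps: 1.87 to 3.64. Equal-length phases: 1.48 to 3.24. Other control layouts: 2.3 to 5.6.
- Linear time in place of six-week categories, in the layouts of the table: 1.66, 2.33 and 2.63.

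Every layout tried with time in the model exceeded both 1.295 and 1.383.

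**4. Illustrative power.** Assume that the base n0 gives 80% at one-sided 0.05, ignoring the interim. Then power = Φ((0.842 + 1.645) × √(2304/(DE × n0)) − 1.645).

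| DE | n0 = 1779 | n0 = 1686 |
|---|---|---|
| 0.999 | 88% | 90% |
| 2 | 64% | 66% |
| 3 | 50% | 51% |

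For example, at DE 2 and n0 = 1779: 2.487 × √(2304/3558) − 1.645 = 0.356, and Φ(0.356) = 0.64.

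**5. Pre-inflation m.** At the final site size, the plan's formula gives DE = 1 + 383 × 0.001 = 1.383, against 1.295 if the base is 1779. The effective size is 2304/1.383 = 1666. Putting DE = 1.383 into the power formula turns the assumed 80% into 77.7% (base 1779) or 79.6% (base 1686).

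**The case against.** The strongest reply is that the harm depends on something the plan does not print. Under Equation 1 as it stands the design effect is about 1.0, so an inflation of roughly 1.3 is conservative, and the absence of a time term is a separate issue. Moreover, the input to Section 7.4 comes from a simulation whose details are not visible. It may already have allowed for calendar time, the allocation and the hurdle outcome. The target power is also hidden, phase lengths vary by site, the dates and share of the retrospective controls are unknown, and a continuous-outcome model only approximates a hurdle model.

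Most of this stands, and it limits what can be said about power. It does not rescue the formula. Whatever the simulation contained, multiplying its result by 1 + (m − 1)ρ treats the sites as if each supplied one arm, and they do not. Conservatism under Equation 1 is also little comfort when Section 3.2 gives change over time as a reason for the design.

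A reader might also infer that 2304 contradicts the plan's own formula because 384 per site gives 1.383. The documents do not support that. The plan defines m as the estimated size, not 384, and 2304 solves backwards cleanly to a base of 1779. Even a base of 1686 with m = 384 gives 1686 × 1.383 = 2332, within 1.2% of a total described as approximate. No arithmetic error is shown.

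**Conclusion.** Wrong as written: the inflation factor in Section 7.4 belongs to a different design and matches neither possible analysis. It is larger than needed for Equation 1 as printed (about 1.30 against about 1.0). It is too small if calendar period is modelled (about 1.30 against about 1.8 to 4.3 in the main illustrative layouts). The direction with time in the model was the same in every layout tried. The exact values rest on the inferred 2:1 allocation, six-week periods, intervention phases of 12 to 36 weeks, and a continuous outcome. The 1.30 rests on solving 2304 backwards.

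It would be tempting to conclude that the trial is underpowered or needs more patients. The documents do not allow that: base size, target power and simulation are not visible, so the power figures above are illustrations on an assumed 80%. The use of m before inflation is a true but minor defect. It would take an assumed 80% to about 78–80%, and it falls away once the formula is dropped.

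**What to change.** Keep 2304 and remove DE = 1 + (m − 1)ρ from Section 7.4. Recompute power by simulation from the actual primary model: the hurdle outcome, site, calendar period, and the planned control:intervention layout including the retrospective controls. Run it over a range of ICCs rather than 0.001 alone. State the assumed phase lengths and allocation. Restate in Sections 7.1 to 7.4 the resulting power and the detectable reduction in transfused volume at 2304.

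The cost is one simulation and possibly a less favourable stated power. No additional patients are involved.

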7.6 Data Analysis

7.6.1 Interim Analysis

One interim data analysis and a final analysis will be performed; the interim analysis will be performed after collecting data on 281 subjects in the intervention group and 562 subjects in the control group.

7.6.2 Statistical Analysis

Data from the intervention group will be compared to the control group for statistically significant changes. For those outcome measures that result in statistically significant differences between the intervention and control, study investigators will evaluate the numerical values of the differences for clinical significance. Any study outcome measures determined to be clinically significant are considered successful. All outcome measures will be reported for each site individually and for all sites pooled. Note, exact numerical values for clinical significance are not able to be pre-determined for all outcome measures, as the clinical setting and subject population targeted by this investigation are novel and are difficult to predict.

7.6.2.1 Summary Statistics and Baseline comparisons:

Descriptive statistics will be estimated for each group. Continuous variables will be described by their means, medians, standard deviations, and interquartile ranges. Categorical variables will be described by their frequencies and percentages. Demographics and baseline clinical measurements will be compared

Evaluation of Impacts of Continuous Non-Invasive Intra-operative Hemoglobin and RPVi Monitoring on Intra-operative and Post-Surgical Clinical Outcomes

BIGT0001 version 2

between the groups using ANOVA to compare the means of the continuous variables and Fisher's exact test / Pearson's chi-squared test (χ^2) to compare the rates of the categorical variables.

7.6.2.2 Study Outcomes Statistical Analysis:

Having measurements collected within clusters (clinical site) creates correlated observations. These correlations invalidate the independence assumption in commonly used univariate and multivariate statistical techniques such as t-tests and multiple linear regression. Generalized Linear mixed models (GLMMs) are a flexible class of models that account for correlated observations and thus are a commonly used method for cluster data analysis. This class of model does not require the normality assumption. Generalized linear mixed models will be used for outcomes following a distribution from the exponential family other than normal.

GLMMs will be used to assess the effect of the intervention on continuous and discrete dependent variables. GLMMs differing with respect to their fixed effects, random effects, and residual covariance matrix will be examined. GLMM generally take the form of Equation 1 for baseline observations.

Equation 1. Generalized Linear mixed model assessing intervention effect for a given outcome:

$$y_{ij} = (\beta_0 + \gamma_{0j}) + \beta_1 * \text{intervention} + \sum_{k=2}^p \beta_k x_k + \varepsilon_{ij} \quad (1)$$

The outcome, y_{ij} is the value of a response variable for the i^{th} individual of the j^{th} cluster (clinical site).

The betas represent fixed effects for the intercept (β_0), intervention coefficient (β_1), as well as coefficients (β_2, \dots, β_p) for other variables to be included in the model (e.g. demographic and clinical variables). The gamma coefficient (γ_{0j}) represents a cluster-specific random intercept. It is assumed that γ_{0j} has a normal distribution with a mean of zero and a variance of $\sigma_{\gamma_0}^2$.

Type III tests will be used to test the null hypothesis that a specific fixed effect equals zero ($H_0 : \beta_k = 0$). Wald z-tests will be used to test for a significant random intercept ($H_0 : \sigma_{\gamma_0}^2 = 0$). Residual and influence diagnostics will be assessed for all models.

Sequential boundary tolerances will be estimated using Lan & DeMets alpha spending function approach. Statistical analysis will be performed using SAS 9.4 (SAS Institute, Cary, NC)

Table 6. Aims, Outcome Measures and Associated Analysis Planned for those Aims.

Aims/Objectives	Outcome Measures	Planned Statistical Analysis
Reduce overall allogenic transfusion - Volume	Volume of allogenic RBC transfused: Intra operatively	Binomial-Gamma hurdle model. We will include intervention group, demographic and clinical data in the model as progresses.
	Volume of allogenic RBC transfused: Post operatively	

Evaluation of Impacts of Continuous Non-Invasive Intra-operative Hemoglobin and RPVi Monitoring on Intra-operative and Post-Surgical Clinical Outcomes

BIGT0001 version 2

Evaluation of Impacts of Continuous Non-Invasive Intra-operative Hemoglobin and RPVi Monitoring on Intra-operative and Post-Surgical Clinical Outcomes

BIGT0001 version 2

Aims/Objectives	Outcome Measures	Planned Statistical Analysis
[REDACTED]	[REDACTED]	[REDACTED]
	[REDACTED]	
	[REDACTED]	
	[REDACTED]	

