3.5.1 Primary

To determine whether the addition of SpHb with In Vivo adjustment and RPVi monitoring using the study device will reduce overall allogenic transfusion, where reduction is defined as the decrease in volume of transfusion of the intervention group relative to control group, intra-operatively.

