3.6 Study Outcome Measures

3.6.1 Primary

Volume (mL) of allogenic red blood cells (RBC) transfused intra-operatively.

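### Section 7.6.2 lets unblinded investigators decide, after seeing significant results, which outcomes count as successful, and in the readable text ties that judgement to no pre-stated value or direction

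*Combined protocol and SAP*

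**What the plan says.** Section 7.6.2 (Statistical Analysis) gives the only readable rule for success.

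- **Step 1, the test.** The rule applies "For those outcome measures that result in statistically significant differences between the intervention and control".
- **Step 2, the judgement.** For those outcomes, "study investigators will evaluate the numerical values of the differences for clinical significance".
- **The label.** "Any study outcome measures determined to be clinically significant are considered successful". The primary outcome is not treated separately.
- **The reason for having no fixed bar.** The section notes that "exact numerical values for clinical significance are not able to be pre-determined for all outcome measures", because the setting and population are new and hard to predict.

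No magnitude appears where the primary aim is defined. In Section 3.5.1, "reduction is defined as the decrease in volume of transfusion of the intervention group relative to control group". Section 3.6.1 gives the outcome as "Volume (mL) of allogenic red blood cells (RBC) transfused intra-operatively", with no minimum difference.

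Section 7.8 fixes the statistical bounds: overall alpha 0.05, one-sided, with 2.5380 at the interim and 1.6621 at the final analysis. It also sends the interim results to the principal investigators, the sponsor and the DSMB. Section 7.9 lets the same three parties end the study if the interim shows statistical significance on the outcome measures. It has no clinical-significance step.

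**The concern.** The people who apply the label know the groups and use the device. In the intervention phase the investigators work with the SpHb and RPVi readings in view (Section 6.2). The principal investigators also see the interim results (7.8), share the stopping decision (7.9) and plan to publish (13.2). Section 3.3 itself accepts that knowing the study objectives may change investigators' behaviour.

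Under 7.6.2 these people decide whether a difference is large enough once they know how large it is. Nothing in the readable text lets a reader check whether the bar was set before or after the result. The rule covers every outcome, so the label can be given selectively among whichever outcomes reach significance. It can also be withheld from a valid primary result. Section 7.6.2 speaks of differences without a direction, although the objective in 3.5.1 and the bounds in 7.8 are one-directional.

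**Working it through.** **1. The bounds reproduce.** Inputs from Section 7.8: one-sided alpha 0.05, O'Brien-Fleming-type Lan-DeMets spending, interim at time 0.5.

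- Alpha spent at the interim: 2 × [1 − Φ(1.960/√0.5)] = 2 × [1 − Φ(2.772)] = 0.00557 (plan: 0.0056), so z = 2.5380 (plan: 2.5380).
- Alpha left: 0.05 − 0.00557 = 0.0444 (plan: 0.0444). With correlation √0.5 between the two statistics, the final z = 1.6621 (plan: 1.6621).

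The statistical step is therefore pre-specified and sound as computed.

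**2. How far below plan a significant result can be.** The assumed effect, the power and the unadjusted sample size are not readable, so the total of about 2304 cannot be rebuilt. The ratio of the smallest significant difference to the planning effect needs only the bounds and the power, so power is taken as an assumption of 80% to 95%.

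Let θ be the planning effect divided by its standard error at the final analysis. Then θ solves

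power = 1 − P(Z₁ < 2.5380 − θ√0.5, Z₂ < 1.6621 − θ), with correlation √0.5.

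The smallest significant observed difference, as a share of the planning effect, is 1.6621/θ at the final analysis and 2.5380/(θ√0.5) at the interim.

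| Assumed power | θ | Final: share of planning effect | Interim: share of planning effect |
|---|---|---|---|
| 80% | 2.496 | 0.67 | 1.44 |
| 85% | 2.691 | 0.62 | 1.33 |
| 90% | 2.937 | 0.57 | 1.22 |
| 95% | 3.301 | 0.50 | 1.09 |

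At the interim, a significant result already exceeds the planning effect. At the final analysis, significance begins at one half to two thirds of it. From that point upward, 7.6.2 leaves the label to judgement. This is a normal approximation, not a calculation under the Binomial-Gamma hurdle model of Table 6.

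**3. The rules side by side.**

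| Place | What makes a result positive |
|---|---|
| 3.5.1 | A decrease in transfused volume; no size given |
| 7.6.2 | Statistical significance, then the investigators' judgement; no value or direction |
| 7.8 | Crossing a one-sided bound |
| 7.9 | Statistical significance on the outcome measures may end the study |

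Section 7.9 is permissive and does not use the word success, so it does not strictly contradict 7.6.2. Even so, the study could end on a result that 7.6.2 would not yet call successful.

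**The case against.** There are four good objections, and each limits the point.

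**The test comes first.** A reader might infer that investigators can declare success at will, or that the type I error is inflated. The text does not support that. Only significant outcomes reach the judgement, so for any single test it can only withhold the label.

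**A value may exist out of sight.** A reader might infer that no threshold is fixed anywhere. Sections 7.1 to 7.3, Table 5 and most of Table 6 are withheld or not shown. The note in 7.6.2 can mean that values are lacking for some outcomes only. What can be said is that 3.5.1, 3.6.1 and 7.6.2 neither state a value nor point to one.

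**A planning effect is not a minimum important difference.** Section 7.4 shows that the sample size came from a simulation, and sizing for power requires an assumed effect. It does not follow that the simulation contains a threshold for clinical importance.

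**The sample size does not make trivial differences pass.** With 2304 split 768 to 1536 (the interim's 1:2 ratio, assumed to hold at the end), the final bound corresponds to 1.6621 × √(1/768 + 1/1536) = 0.0735 SD. The plan's own design effect with m = 2304/6 = 384 is 1 + 383 × 0.001 = 1.383, which raises this to 0.0735 × √1.383 = 0.086 SD. The readable text gives no SD and no control mean, so this cannot be turned into mL or called small. A result at 50% to 67% of plan is below plan, but that does not make it trivial.

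None of these supplies what 7.6.2 lacks: a stated reference for the judgement that decides the label.

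**Conclusion.** The point holds in a limited form. For every outcome including the primary, 7.6.2 makes success depend on unblinded investigators' judgement after significant differences are known, and the readable text links that judgement to no pre-stated value or direction. The damage is to the credibility of the conclusion: a success label that cannot be verified, may be applied to any significant outcome, and sits beside a stopping provision in 7.9 with a different criterion. The error rate of a single test is not affected.

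The range left to judgement at the final analysis starts at about 67% (80% power) to 50% (95% power) of the planning effect and has no upper limit. These figures rest on the assumed power, the Table 7 bounds with the interim at time 0.5, and a normal approximation. The conclusion about the rule itself needs none of these assumptions.

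**What to change.** Make these changes before the interim analysis.

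1. In 7.6.2, define primary success as crossing the one-sided Table 7 bound in the direction of reduced intra-operative RBC volume. Name the statistic that is compared with the bound, since the hurdle model in Table 6 has two parts.
2. Separately, report the estimated difference in mL with its confidence interval, and read clinical relevance against a value stated in advance. The effect assumed in the sample-size simulation could serve; say whether it is regarded as a minimum important difference. If a value already stands in withheld text, 7.6.2 should refer to it.
3. For all other outcomes, report estimates with confidence intervals and drop the success label.
4. Reconcile 7.6.2 with 7.9, so that both use the same definition of a positive result and say which outcome it concerns.

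This changes wording only, with no new data and no change in sample size. The cost is that the investigators and the sponsor give up discretion over the label. A significant effect smaller than planned would then count as a statistical success automatically. The change does not prevent that, but it shows such a result openly against the pre-stated value.
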